5.11.2.6. CGM Targets of Glycemic Control

According to the guidance (Battelino 2019), the following CGM targets of glycemic control will also be derived during a 24-hour period.

- The percentage of time within a normal glycemia range (defined as between 70 mg/dL and 180 mg/dL [3.9 and 10.0 mmol/L]) $>70\%$
- The percentage of time within a hypoglycemic range (defined as defined as <70 mg/dL [3.9 mmol/L]) $<4\%$
- The percentage of time within a hypoglycemic range (defined as defined as <54 mg/dL [3.0 mmol/L]) $<1\%$
- The percentage of time within a hyperglycemic range (defined as >180 mg/dL [10.0 mmol/L]) $<25\%$
- The percentage of time within a hyperglycemic range (defined as >250 mg/dL [13.9 mmol/L]) $<5\%$

5.11.3. Definition of Variables

In this section, we define the derived variables that are used for the analysis in Section 5.11.2 and some additional variables that may be used for exploratory analyses.

5.11.3.1. Glucose in Target Ranges, Hypoglycemia or Hyperglycemia

The percentage of time within a glucose range (target, hypoglycemia or hyperglycemia ranges) will be calculated as the number of observations within the specified range divided by the number of observations in the time interval (for example, 24-hour period). The duration (in minutes) within the glucose range will then be calculated as the percentage of time within the

glucose range times the length of the period (24 hour, 18 hour, and 6 hour, for the periods of 24 hour, daytime or nighttime, respectively).

5.11.3.2. Hypoglycemic Episode

The CGM-determined hypoglycemic episode is defined as glucose <54 mg/dL (or <70 mg/dL) for at least 15 minutes.

The duration of each episode will be calculated using the time difference between the 2 time points before the incidence starts and after the incidence ends.

The average duration will be calculated by dividing the sum of the duration of individual episodes during the given visit by the number of episodes.

The CGM-determined nighttime hypoglycemic episode is defined as hypoglycemic episodes that occur between 2400 hours and 0600 hours. To calculate the duration of nighttime hypoglycemic episode, the end date/time will be the end date/time when the patient passes outside the hypoglycemic range even if it is outside the interval of 2400 hours and 0600 hours.

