Pharmacokinetics 
 To characterize the PK of LY3209590 in study participants with T1DM 	
 LY3209590 population-based parameters, such as AUC within dosing interval at Weeks 12 and 26
Tertiary/Exploratory	

 To establish the equivalent dose of LY3209590 relative to insulin degludec To investigate the safety and tolerability of LY3209590 compared with insulin degludec in study participants with T1DM 	
 Insulin dose at baseline and Week 26 Treatment-emergent AEs Incidence and rate of hypoglycemia events during the post-treatment follow-up period Discontinuation of IP due to AEs Clinical laboratory results Systematic assessment of injection site reactions Insulin dose for prandial as well as basal insulin during treatment period and follow-up period Incidence and rate of hypoglycemia during treatment and follow-up period

Objectives	Endpoints
	
 • Incidence and rate of daytime hypoglycemia • Liver aminotransferase change from baseline to Weeks 12 and 26 • Triglyceride and FFA change from baseline to Weeks 12 and 26 • Body weight change from baseline to Weeks 12 and 26

 • To explore quality of glycemic control compared with insulin degludec using CGM 	
 • Glucose time in target range, time in hyperglycemia, time in hypoglycemia • Duration of hypoglycemic events

 • To establish the relationships between dose/exposure and key safety and efficacy measures for LY3209590 	
 • LY3209590 exposure-response relationships for key efficacy and safety measures (e.g., glycemic control, hypoglycemia and safety labs).

 • To characterize the effects of LY3209590 on exploratory PD biomarkers • To explore the development of LY3209590 ADAs • To explore the compliance with the dosing regimen 	
 • Lipids (cholesterol, LDL, HDL, triglycerides) • 6-point SMBG glucose profiles • Biomarkers of lipolysis (FFA) • The frequency of antibody formation to LY3209590 and relationship to safety and efficacy markers will be determined • Incidence and percentage of missed doses of LY3209590 and insulin degludec.

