5.11. Continuous Glucose Monitoring Analysis

5.11.1. General Consideration

For all study participants meeting study entry criteria, a CGM device will be inserted and activated at (Visit 2). Patients will be unblinded to the CGM system and wear the study provided CGM during the study duration.

All participants who are randomized to either LY3209590 Algorithm 1 or insulin degludec, receive at least 1 dose of study treatment, and have evaluable CGM data from baseline and at least 1 postbaseline will be included in the analyses. The data collected after permanent discontinuation of the IP will be censored. There will be no multiplicity adjustment. Additional analysis may be conducted to compare between the LY3209590 (by pooling LY3209590 Algorithm 1 and LY3209590 Algorithm 2) and insulin degludec if deemed necessary.

According to the 2020 American Diabetes Association standard of medical care in diabetes, the CGM data will be included in the analysis only if at least 70% of the total measures in the analysis period are obtained (defined as a valid CGM period). For example, the 24-hour period will have 288 measures and the minimum number of measures will be 202. All the CGM derivations are based on the data from valid CGM period unless otherwise specified.

The CGM variables will be derived for each CGM day when the analysis data meet the above requirement. The derived variables for a visit will be based on the daily CGM variables within the given visit. Also, the CGM variables will be derived for the following analysis periods: baseline (using data prior to the first dose date), 0-12 Week, 12-26 Week and 0-26 Week of treatment period.

Summary statistics will include the number of observations, mean, median, maximum, minimum, and SD for all continuous measures. For categorical measures, the number of observations, proportion, and frequency will be included in summary statistics. All analyses will be performed by visit and treatment.

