5.11.2. CGM Variables and Analysis

The continuous variables derived from CGM will be summarized and compared between treatment groups by visit using MMRM model. The model will include the treatment, HbA1c stratum (<8.5% or >=8.5%), baseline value of the dependent variable, visit, and treatment by

visit interaction. The raw mean and LS mean difference between treatment groups will be summarized.

For the between-day and within-day glucose variability, the variable will take log-transformation before performing the MMRM analysis.

The binary variables will be analyzed using a longitudinal logistic regression. In the longitudinal logistic regression model, the independent variables of treatment, baseline HbA1c value, baseline continuous variable corresponding to the binary dependent variable, visit, and treatment by visit interaction will be used.

For the hypoglycemia episodes defined by CGM, the analysis using a negative binomial model with the offset of log (exposure in year) will be performed. The model will include treatment, baseline HbA1c, baseline incidence for the dependent variable.

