5.11.2.1. Hypoglycemia

- Percentage and Duration (in minutes) of time per day where glucose values are within a hypoglycemic range (defined as <70 mg/dL [3.9 mmol/L]) during the nighttime period (defined as midnight to 0600 hours), the daytime period (defined as 0600 hours to 2400 hours) and a 24-hour period.
- Percentage and Duration (in minutes) of time per day where glucose values are within a hypoglycemic range (defined as <54 mg/dL [3.0 mmol/L]) during the nighttime period, the daytime and a 24-hour period.
- Percentage and Duration (in minutes) of time per day where glucose values are within a hypoglycemic range (defined as <70 mg/dL [3.9 mmol/L] and ≥ 54 mg/dL [3.0 mmol/L]) during the nighttime period, the daytime period and a 24-hour period.
- Incidence of hypoglycemic episodes (defined as <70 mg/dL [3.9 mmol/L], or <54 mg/dL [3.0 mmol/L] or <70 mg/dL [3.9 mmol/L] and ≥ 54 mg/dL [3.0 mmol/L]) during the nighttime period, the daytime period and a 24-hour period.
- Rate of hypoglycemic episodes (defined as <70 mg/dL [3.9 mmol/L], or <54 mg/dL [3.0 mmol/L] or <70 mg/dL [3.9 mmol/L] and ≥ 54 mg/dL [3.0 mmol/L]) during the nighttime period, the daytime period and a 24-hour period.
- Duration (in minutes) of each individual hypoglycemic episode (defined as <70 mg/dL [3.9 mmol/L], or <54 mg/dL [3.0 mmol/L] or <70 mg/dL [3.9 mmol/L] and ≥ 54 mg/dL [3.0 mmol/L] for at least 15 minutes).

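### Average CGM episode duration has no baseline value for participants without a lead-in episode, so the planned MMRM would drop them from the model-based duration comparison

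*SAP*

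**What the plan says.** Protocol Section 3 lists "Duration of hypoglycemic events" as a tertiary/exploratory endpoint under the CGM objective. Section 2.2 explains the interest: a longer duration of lows is named as a theoretical downside of a once-weekly insulin.

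SAP Section 5.11.2.1 lists "Duration (in minutes) of each individual hypoglycemic episode" among the CGM variables, for <70, <54 and 54 to <70 mg/dL. Section 5.11.3.2 sets the event: "The CGM-determined hypoglycemic episode is defined as glucose <54 mg/dL (or <70 mg/dL) for at least 15 minutes". It then forms one value per visit by "dividing the sum of the duration of individual episodes during the given visit by the number of episodes".

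Section 5.11.2 gives the model: "The continuous variables derived from CGM will be summarized and compared between treatment groups by visit using MMRM model". Its terms are treatment, HbA1c stratum, then "baseline value of the dependent variable, visit, and treatment by" visit interaction. The negative binomial model in the same section has an exposure offset and is for episode counts, so it does not cover duration.

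Section 5.11.1 takes CGM baseline from data before the first dose. It admits participants who have evaluable CGM data at baseline and at least once afterwards; it does not require an episode. Neither document gives a rule for a period with no episode.

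**The concern.** The per-visit average exists only if the participant had an episode in that period. Used as a baseline covariate, it is missing for anyone whose lead-in had no low lasting at least 15 minutes. The baseline covariate is the same on all of a participant's rows, so a mixed model that needs complete covariates removes all of them, including visits where an episode occurred and its duration was measured.

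The adjusted treatment comparison of duration would then rest only on participants who were already having lows before randomization. Participants whose first CGM lows come during treatment would not contribute to it, although the protocol's question about prolonged lows concerns them too. Running the model as written gives up usable data on a protocol endpoint, and the SAP does not say that this is intended.

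**Working it through.** **The plan's own figures.** The SAP states no sample size or precision for the duration analysis. The one figure in its CGM rules that can be checked reproduces: 0.70 × 288 = 201.6, so at least 202 readings per 24 hours.

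**Reading the definitions together.**
1. Average duration = (sum of episode durations) / (number of episodes). With no episodes this is 0/0.
2. CGM starts at Visit 2 (Week -1, window ±3 days) and randomization is at Week 0. The baseline period is therefore nominally 7 days, about 4 to 10.
3. A participant with valid wear and no episode in that period meets Section 5.11.1 but has no baseline value for Section 5.11.2.
4. The SAP's example code for the primary analysis uses PROC MIXED, which omits rows with a missing covariate. All of this participant's rows go.

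**Size.** The documents give no CGM episode rate, so the rate *r* per week is assumed. Further assumptions are a 7-day lead-in and four one-week post-baseline windows. Let P0(μ) be the probability of no episode when μ are expected:
- Poisson: P0(μ) = exp(−μ)
- Negative binomial with dispersion *k* (a participant keeps the same underlying rate throughout): P0(μ) = (1 + kμ)^(−1/k)

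Someone with no post-baseline episode has no duration to lose. The relevant share is therefore taken among participants with at least one defined post-baseline duration:

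loss = [P0(r) − P0(5r)] / [1 − P0(4r)]

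For Poisson this reduces to exp(−r). Worked example, r = 1 and k = 2: P0(1) = 3^(−1/2) = 0.577, P0(5) = 11^(−1/2) = 0.302, P0(4) = 9^(−1/2) = 0.333, so loss = (0.577 − 0.302) / (1 − 0.333) = 0.41.

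| Episodes per week | No lead-in episode, all participants (Poisson to k = 2) | Loss, Poisson | Loss, k = 1 | Loss, k = 2 |
|---|---|---|---|---|
| 0.5 | 61% to 71% | 61% | 57% | 54% |
| 1 | 37% to 58% | 37% | 42% | 41% |
| 2 | 14% to 45% | 14% | 27% | 30% |
| 4 | 2% to 33% | 2% | 16% | 21% |

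As a check, one simulated data set (238 participants, r = 1, k = 1) lost 68 of 175 participants with a usable post-baseline duration, or 39%, against 42% from the formula.

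**Sensitivity to the windows.** Replacing 4 and 5 by 26 and 27 in the formula, for continuous wear over the whole treatment period, gives at r = 1 and k = 2: (0.577 − 55^(−1/2)) / (1 − 53^(−1/2)) = (0.577 − 0.135) / (1 − 0.137) = 0.51. Longer windows move the loss towards the all-participant share.

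**Precision.** By participant count, a 40% loss multiplies the confidence interval width by 1/√0.60 = 1.29, about 29% wider.

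**The case against.** Several points on the other side stand.

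- **The SAP does not state that rows are deleted.** It is the standard behaviour of the software named, not a written rule. An unwritten convention, such as zero minutes for no episode, would keep these participants but change what the variable means. Either way a written rule is needed.
- **Average duration might not be meant for the model.** Section 5.11.2.1 names the duration of each episode, and Section 5.11.3 says it also defines variables that may be only exploratory. But a by-visit MMRM needs one value per visit, and the average is the only such summary of episode duration defined.
- **No episode rate is documented.** The assumed range spans a trivial loss and a large one. Nothing in the documents shows that lead-ins without an episode are common.

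A reader might also infer stronger things that the documents do not support:

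- *That lows first appearing on study drug vanish from the report.* Section 5.11.1 gives by-visit descriptive statistics for all continuous CGM measures, and Section 5.11.2 reports raw means. Neither needs a baseline duration.
- *That the comparison is biased between arms.* The exclusion is on a pre-randomization feature. It narrows the population and costs precision, but does not by itself unbalance the arms.
- *That the loss equals the share of all participants without a lead-in episode.* That denominator includes people with no post-baseline duration to lose.
- *That no other CGM analysis would show more or longer lows.* Section 5.11.2.1 analyses percentage and minutes of time below range, which are defined at zero, as well as episode incidence and rate.

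**Conclusion.** The point holds for the model-based comparison of average episode duration only. The definition, the model term and the inclusion rule do not fit together, and no text resolves the zero-episode case. Under standard missing-covariate handling, participants without a lead-in episode drop out at every visit.

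Under the assumptions above, the loss among those with a usable post-baseline duration is about 54% to 61% at 0.5 episodes per week, 37% to 42% at 1, 14% to 30% at 2 and 2% to 21% at 4. The consequence is mainly lost precision and a narrower population. The primary HbA1c analysis is untouched.

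A separate limitation remains: average duration is also undefined at any post-baseline visit without an episode, so the comparison conditions on an event after randomization whatever baseline covariate is used. Because the endpoint is exploratory, the priority is low.

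**What to change.** In SAP Section 5.11.2, for average episode duration only, replace the baseline value of the dependent variable with the lead-in percentage of time in the matching glucose range: <70, <54, or 54 to <70 mg/dL. Section 5.11.2.1 already derives these percentages, and they are defined for everyone with valid baseline CGM, whether or not an episode occurred. They need not be zero without an episode, because Section 5.11.3.1 counts every low reading while an episode needs at least 15 minutes; this does not matter for use as a covariate.

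The change keeps every participant with valid baseline CGM and at least one post-baseline episode. Add that visits without an episode remain undefined, so that the comparison is conditional on having an episode and is to be read beside the time-below-range and episode-rate analyses.

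The cost is a sentence or two of SAP text and no new derivation. The downside is that the substitute covariate may predict duration slightly less well among participants who did have lead-in episodes.

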5.11.3.3. Glycemic Variability

Glycemic variability will be evaluated using the notation below:

i represents a time point within a time period (a 24-hour period, daytime or nighttime)

n represents the number of time points within the time period

k represents a day within a visit

m represents number of days CGM is performed at a visit

$BG_{k,i}$ represents the glucose value at time point i on day k unless otherwise specified.

- Within-Day Variability

For variables assessing within-day variability, first determine the variability within each day, then average across days within a visit.

Within-day glucose SD (Rodbard 2009):

$$SD = \frac{1}{m} \sum_{k=1}^m SD_k = \frac{1}{m} \sum_{k=1}^m \sqrt{\frac{\sum_{i=1}^n (BG_{k,i} - \bar{BG}_{k,i})^2}{n-1}}$$

Within-day glucose CV (Clarke and Kovatchev 2009):

$$CV = \frac{1}{m} \sum_{k=1}^m CV_k = \frac{1}{m} \sum_{k=1}^m \frac{SD_k}{\bar{BG}_{k,i}} \times 100$$

The LBGI, HBGI, and BGRI will be calculated using the standard formulas.

The LBGI has been developed to quantitate both frequency and severity of hypoglycemia. The LBGI has been validated as a predictor of severe hypoglycemia, which is an SAE and could result in coma or death if unrecognized and untreated. The HBGI quantifies both frequency and severity of hyperglycemia and has been related to HbA1c and risk for hyperglycemia (Kovatchev et al. 2006). Additionally, both the LBGI and HBGI have a high sensitivity to changes in glycemic profiles and control (Kovatchev et al. 2006). LBGI is a non-negative number that increases as the number of low readings increases. HBGI is a non-negative number that increases as the number of high readings increases.

The LBGI, HBGI, and BGRI will be derived for each day of a visit and then average across days within a visit. The calculations of LBGI, HBGI and BGRI take the following steps:

Step 1: For each blood glucose (BG [mg/dL]) at the i^{th} time point, compute the following:

$$f(BG_i) = 1.509 \times [(\ln(BG_i))^{1.084} - 5.381]$$

This transforms the BG data using a nonlinear transformation that maps the BG range of 20 to 600 mg/dL to a symmetric interval of $(-\sqrt{10}, \sqrt{10})$

The center of the BG scale is 112.5 mg/dL and is mapped to 0

Step 2: Compute BG risk for each reading

$$rl(BG_i) = 10 \times f(BG_i)^2 \text{ if } f(BG_i) < 0; \text{ otherwise } rl(BG_i) = 0$$

$$rh(BG_i) = 10 \times f(BG_i)^2 \text{ if } f(BG_i) > 0; \text{ otherwise } rh(BG_i) = 0$$

Assign the risk of each BG value by applying the above quadratic risk function

Value range from 0 (achieved when BG = 112.5, the center) to 100

Left side of the parabola is risk of hypoglycemia, and the right side is risk of hyperglycemia

Step 3: Compute LBGI and HBGI

$$LBGI = \frac{1}{n} \sum_{i=1}^n rl(BG_i)$$

$$HBGI = \frac{1}{n} \sum_{i=1}^n rh(BG_i)$$

Step 4: Compute BGRI

$$BGRI = LBGI + HBGI$$

- Between-Day Variability

For variables assessing between-day variability, first determine the variability for each time point across days within a visit then average across all time points.

Between-day glucose SD (Rodbard 2009):

$$SD = \frac{1}{n} \sum_{i=1}^n SD_i = \frac{1}{n} \sum_{i=1}^n \sqrt{\frac{\sum_{k=1}^m (BG_{k,i} - \left\{ \frac{\sum_{k=1}^m BG_{k,i}}{m} \right\})^2}{m-1}}$$

Between-day glucose CV (Kovatchev et al. 2009):

$$CV = \frac{1}{n} \sum_{i=1}^n CV_i = \frac{1}{n} \sum_{i=1}^n \frac{SD_i}{\left(\frac{\sum_{k=1}^m BG_{k,i}}{m} \right)} \times 100$$

Mean of daily differences (MODD): this parameter is calculated as the mean of absolute differences between glucose values at corresponding time points of consecutive days.

$$MODD = \frac{1}{m-1} \sum_{k=1}^{m-1} \frac{\sum_{i=1}^n |BG_{k+1,i} - BG_{k,i}|}{n}$$

5.12. Subgroup Analyses

The subgroups will be defined as:

- Body mass index (<30, ≥ 30)
- Baseline HbA1c (<8.5% and $\geq 8.5\%$)
- Region (US and non-US)

The outcome measures included in the subgroup analyses are:

[figure not shown]
- HbA1c and change in HbA1c from baseline to up to 26 weeks
- Documented hypoglycemia, non-nocturnal and nocturnal hypoglycemia rates (<54 mg/dL [3.0 mmol/L]) during 0-26 weeks.

Analyses for HbA1c and its change will be performed examining the 3-way interaction of the primary treatment arms, visit and the subgroup variable using the same MMRM model described for the primary analysis. This model will include the same fixed effects given for the primary analysis model plus factors of subgroup, 2-way interaction of subgroup and treatment, 2-way interaction of subgroup and visit, and 3-way interaction of treatment, visit and the subgroup.

The hypoglycemia rates will be analyzed using a negative binomial regression including the same fixed effects for hypoglycemia event analyses plus factors of subgroup, 2-way interaction of subgroup and treatment.

The interaction effects will be evaluated using a significance level of 0.1, unadjusted. If the interaction effect is significant ($p<0.1$), separate analysis without the terms related with the subgroup will be performed for each subpopulation.

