Treatment comparisons will be performed by the treatment difference in least-squares means (LS mean). Means and LS mean by treatment group and visit, along with the standard error of LS mean, 90% CIs of the treatment differences along with the p-value for the treatment comparison will be displayed. For the change from baseline, p-value for the within-treatment comparison will also be displayed. For selected parameters, log-transformed values will be analyzed in the MMRM model instead. The actual, change from baseline and percentage change from baseline will be presented using the derivation based on the output from the MMRM model.

In this study, the negative binomial regression will estimate Group Mean instead of LS mean and use delta method to estimate the standard error of the Group Mean (Qu and Luo 2015). Group Mean is defined as the mean response in the treatment group for the studied population. The difference between LS mean and the Group Mean is that LS mean estimates the response by

taking the inverse link function on mean covariates, while the Group Mean takes the inverse link function on individual patient covariates first and then averages over all patients.

Sensitivity analyses may be conducted for selected safety and efficacy measures by excluding data from patients who significantly deviated from the study dose algorithm, for example patients who received repeated loading doses. The study team will review patient study dose data and identify the patients who will be excluded from the sensitivity analyses prior to the final lock of the study data.

All analyses will be implemented using SAS Enterprise Guide Version 7.1 or above.

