5.7. Primary Outcome and Methodology

The primary objective is to compare the HbA1c change from baseline to Week 26 between LY3209590 and insulin degludec and will be based on the primary estimand described below.

The primary estimand is the treatment differences in the change in HbA1c from baseline to 26 weeks for the targeted study population if all patients would adhere to the treatment without intercurrent events. The analysis data will include data up to the discontinuation of study treatment for the Efficacy Population with baseline and at least one non-missing postbaseline measurement. There may be missing values due to the early discontinuation of study treatment. The MMRM model will be used with the HbA1c changes at Week 6, 12, 16 and 26 (the primary endpoint) and the missing values will be imputed implicitly in the MMRM analysis under the assumption of missing at random. The MMRM model will include treatment (LY3209590 Algorithm 1, insulin degludec), country, visit, and treatment by visit interaction and the baseline value of the dependent variable as the fixed effects. The HbA1c is reported in unit of % and will be converted to the unit of mmol/mol using the following formula: HbA1c in mmol/mol = 10.93*HbA1c in % - 23.5 (<http://www.ngsp.org/ifccngsp.asp>). HbA1c analysis will be conducted based on both units.

In the MMRM model, the within-patient errors are modeled as an unstructured variance-covariance matrix. If the analysis fails to converge, the following variance-covariance matrix will be used (in order) until one converges:

1. Toeplitz with heterogeneity
2. autoregressive with heterogeneity
3. compound symmetry with heterogeneous variances
4. Toeplitz
5. autoregressive
6. compound symmetry without heterogeneous variances

The Kenward-Roger approximation will be used to estimate denominator degrees of freedom for the MMRM models. The following is an example SAS code:

```
proc mixed data=DATA;
  class TREATMENT STRATIFICATIONS VISIT PATIENT;
  model HbA1c=BASELINE TREATMENT STRATIFICATIONS VISIT
    VISIT*TREATMENT / solution ddfm=kr;
  repeated VISIT / subject=PATIENT type=un;
  lsmeans TREATMENT*VISIT/ pdiff cl alpha=0.1 om=DATA;
run;
```

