The 2-sided 90% CI of the LS mean for individual treatment groups, treatment LS mean difference (LY3209590 Algorithm 1 versus insulin degludec) in the HbA1c change from baseline to Week 26 will be estimated. Similar analysis based on the above MMRM model will also be provided for the comparison between LY3209590 (by pooling LY3209590 Algorithm 1 and LY3209590 Algorithm 2) and insulin degludec.

With the primary estimand, LY3209590 Algorithm 1 will be declared noninferior to insulin degludec if the upper limit of the 2-sided 90% CI for the LS mean difference in the HbA1c change from baseline is below +0.4%.

A supportive estimand is the treatment differences in HbA1c change from baseline to Week 26 for the targeted study population regardless of the use of rescue medication or taking study medication. The analysis data will include all available data at Week 26 regardless of treatment disposition status for all randomized patients who took at least one dose of study treatment and have non-missing baseline. There will be missing endpoint due to early study discontinuation. The missing endpoint will be imputed by “return to baseline” imputation. Multiple imputations will be conducted and an analysis of covariance model including factors of treatment and country, and baseline HbA1c as covariates will be performed by imputation data set. Then, the inference will be based on bootstrap method.

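### The HbA1c subgroup test in SAP 5.12 asks whether a subgroup difference changes over visits, not whether the Week 26 treatment effect differs between subgroups

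*SAP*

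**What the plan says.** SAP 5.12 defines three two-level subgroup variables: BMI, baseline HbA1c and region. For HbA1c it states: "Analyses for HbA1c and its change will be performed examining the 3-way interaction of the primary treatment arms, visit and the subgroup variable". The model is the primary MMRM "plus factors of subgroup, 2-way interaction of subgroup and treatment, 2-way interaction of subgroup and visit, and 3-way interaction of treatment, visit and the subgroup". On the decision rule: "The interaction effects will be evaluated using a significance level of 0.1, unadjusted". If the interaction is significant, "separate analysis without the terms related with the subgroup will be performed for each subpopulation". The rule does not say which interaction term it means, but the 3-way term is the only one that 5.12 says is examined for HbA1c. For hypoglycemia rates the model has only the 2-way subgroup-by-treatment term, so the point is confined to HbA1c.

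In SAP 5.7 the MMRM uses HbA1c changes at Weeks 6, 12, 16 and 26, and the primary result is at the last of these: "treatment LS mean difference (LY3209590 Algorithm 1 versus insulin degludec) in the HbA1c change from baseline to Week 26 will be estimated". The default display in SAP 5.1 is "Means and LS mean by treatment group and visit, along with the standard error of LS mean", and the example code in 5.7 has "lsmeans TREATMENT*VISIT/ pdiff cl alpha=0.1 om=DATA". Neither is by subgroup. No treatment-by-subgroup contrast at Week 26 is named.

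**The concern.** The primary estimate and the non-inferiority decision are at Week 26. The matching subgroup question is whether the Week 26 treatment difference varies with BMI, baseline HbA1c or region, and the 3-way term does not ask it. Once subgroup-by-treatment is in the model, the 3-way term carries only the departure of the subgroup difference from a constant over visits. It can be null when a real Week 26 difference exists, and far from null when none does.

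The separate analyses are the only by-subgroup HbA1c results that 5.12 commits to, and they sit behind this test. A steady difference would usually go unreported, while an early one that had disappeared could lead to separate analyses and be read as bearing on the primary endpoint.

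**Working it through.** **Inputs from the documents.** 95 completers per arm, SD 1.1%, margin 0.4%, true difference 0, two-sided alpha 0.1 (protocol 9.2); visits at Weeks 6, 12, 16 and 26 (SAP 5.7); interaction level 0.1 (SAP 5.12).

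**Assumed, not in the documents.** Two subgroups of equal size (25:75 as a variant), SD 1.1% at every visit, complete data, and five correlation structures: 0.9 or 0.8 per 4 weeks, and exchangeable 0.5, 0.7 or 0.85.

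**The plan's own figure.** SE = 1.1 × √(2/95) = 0.160. 0.4/0.160 = 2.51, and 2.51 − 1.645 = 0.86, giving power of 80.5%. 238 × 0.8 = 190 completers. The stated 80% reproduces. The documents give no operating figure for the subgroup test.

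**What each term tests.** Let δ6, δ12, δ16, δ26 be the difference between subgroups in treatment effect at each visit.
- 3-way term (3 df): δ6 = δ12 = δ16 = δ26.
- 2-way subgroup-by-treatment term as a Type 3 test (1 df): the mean of the four δ is 0.
- Week 26 contrast (1 df): δ26 = 0.

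If all four δ are equal, the 3-way null hypothesis is true exactly, whatever the size, split or correlation.

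**Power.** Each test is referred to a noncentral F with 186 residual df.
- SE of the Week 26 contrast: 1.1 × √(4/47.5) = 0.319% with equal subgroups; 1.1 × √(2/23.75 + 2/71.25) = 0.369% at 25:75.
- Week 26 contrast at 0.6%: noncentrality (0.6/0.319)² = 3.53, power 0.59.
- 3-way term under exchangeable correlation ρ: noncentrality = Σ(δ − mean δ)² / [SE² × (1 − ρ)]. For 0.6% at Week 26 only and ρ = 0.7: 0.27 / (0.102 × 0.3) = 8.8, power 0.80. The mirror pattern (0.6% at the first three visits, then 0) has the same sum of squares and the same power.

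Chance of p<0.1 for a 0.6% difference, equal subgroups, range over the five correlation structures:

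| Pattern over Weeks 6/12/16/26 | 3-way term | 2-way, averaged | Week 26 contrast |
|---|---|---|---|
| Constant | 0.10 | 0.63–0.77 | 0.59 |
| Early build-up (50/80/90/100%) | 0.18–0.42 | 0.48–0.60 | 0.59 |
| Growth in proportion to week | 0.25–0.72 | 0.31–0.39 | 0.59 |
| Week 26 only | 0.51–0.98 | 0.14–0.16 | 0.59 |
| Weeks 6–16, gone by Week 26 | 0.51–0.98 | 0.44–0.55 | 0.10 |
| Declining (100/75/50/0%) | 0.36–0.92 | 0.30–0.38 | 0.10 |

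A simulation of 6000 trials per case with the unstructured covariance estimated agrees. For a constant 0.6% difference the 3-way term gave 0.10 and the Week 26 contrast 0.58 to 0.60; for a constant 1.0% difference, 0.09 to 0.10 and 0.93; for 0.6% gone by Week 26, 0.74 to 0.80 and 0.10.

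**Limits of the Week 26 contrast.** Its power for differences of 0.4, 0.6 and 0.8% is 0.35, 0.59 and 0.80 with equal subgroups, and 0.29, 0.49 and 0.70 at 25:75. The half-width of a subgroup's own 90% CI is 1.653 × 1.1 × √(2/47.5) = 0.37% with equal subgroups; at 25:75 it is 0.53% in the smaller and 0.30% in the larger.

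**The case against.** The strongest reply is that the trigger sentence names no term. It speaks of interaction effects in the plural, covers both HbA1c and hypoglycemia, and the 2-way term is in both models. If the 2-way term counts, a constant 0.6% difference is found with probability 0.63 to 0.77, better than the Week 26 contrast. If either term counts and the two tests are treated as independent, that rises to between 1 − 0.9 × 0.37 = 0.67 and 1 − 0.9 × 0.23 = 0.79. It is true that the term is unnamed, so the 10% figure depends on the 3-way reading, which is the natural one because 5.12 names that term for HbA1c. The alternatives do not cure the problem. The averaged 2-way test finds a Week-26-only difference with probability 0.14 to 0.16 and flags one that has gone by Week 26 with probability 0.44 to 0.55. An either-term rule has a false-positive rate of about 1 − 0.9² = 0.19.

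Second, the subgroup outcome in 5.12 runs up to 26 weeks, so an early difference is within scope. That stands as a reason to keep a time-course check, but not as a substitute for a Week 26 test.

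Third, an exactly constant difference is a boundary case when doses are titrated weekly for 12 weeks, and the 3-way term is the stronger test for a late difference in most of the structures tried. Both are fair. Even so, with early build-up the 3-way term reaches only 0.18 to 0.42 against 0.59.

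Fourth, the fitted model can already supply Week 26 subgroup estimates, and SAP 5.1 allows additional exploratory analyses. It can, but nothing commits the sponsor to report them.

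**Conclusion.** The concern holds. On the natural reading of SAP 5.12, the HbA1c subgroup test does not address the Week 26 difference, and the reporting of subgroup results depends on it. That a constant difference is flagged only at the alpha level is exact and needs no assumption about correlation or split. The other figures depend on the assumed splits, correlations, constant SD and complete data, but the pattern is the same across all the structures tried. The Week 26 contrast is not uniformly more powerful; its advantage is that it tests the question posed by the primary endpoint. The subgroup analyses are supportive and unadjusted, and the non-inferiority conclusion does not depend on them, so this is a low-priority improvement.

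**What to change.** In SAP 5.12:

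1. Name the treatment-by-subgroup contrast at Week 26, from the MMRM already specified, as the HbA1c interaction test at 0.1.
2. Keep the 3-way term as a descriptive check of time course.
3. State that the Week 26 treatment difference with its 90% CI will be reported for each subgroup from the full model, whatever the interaction p-value. Because the contrast has limited power, these estimates matter more than the test.

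The cost is two or three sentences, plus one ESTIMATE or LSMESTIMATE statement and one by-subgroup LSMEANS line per subgroup variable. No extra data are needed, and protocol Section 9 describes no subgroup analysis that would have to change. The price is some power: against the 3-way term for a late-only difference in most structures (and for steady growth at exchangeable correlation 0.85), and against the averaged 2-way term for a constant difference.
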